13 STUDY INTERVENTION

13.1 Study intervention description

The intervention combinatorial proteins (CP) meals will comprise three isocaloric (810 kcal) and isonitrogenous (22g protein) with stepwise increases in DIAAS (DIAAS: 50%, 75%, and 100%). Intervention foods will be commercially bought and stored at the lab location. An in-depth overview of the macronutrient and caloric composition of the three meals is shown in Table 1.

- CP1: Chickpeas, Quinoa, Quorn, and Bread (DIAAS 105%)
- CP2: Chickpeas, Quinoa, Tofu, and Bread (DIAAS 75%)
- CP3: Chickpeas, Quinoa, and Bread (DIAAS 50%)

	CP1	CP2	CP3
Bread, g	62	147	230
Chickpeas, g	30	44	54
Quinoa, g	55	22	23
Quorn, g	104		
Tofu, g		26	
DIAAS, %	105	75	50
First limiting amino acid	Lysine	Lysine	Lysine
Protein, g	22	21	22
Protein, kcal	88	84	88
Ingested IAA, g	9	9	9
Digested IAA, g	8	8	8
Ingested Leu, g	1.6	1.6	1.6
Digested Leu, g	1.5	1.5	1.5
Ingested Lys, g	1.2	0.9	0.7
Digested Lys, g	1.1	0.8	0.5
Carbohydrates, g	131	132	131
Carbohydrates, kcal	524	528	524
Fats, g	22	22	22
Fats, kcal	198	198	198
Fiber, g	13	7	9
Total kcal	810	810	810

Table 1: An overview of the macronutrient and caloric composition for the intervention meals with an overview of ingested and bioavailable IAAs, Leu (leucine), and Lys (lysine).

13.1.1 *Composition*

The macronutrient composition of each meal will consist of ~810 kcal using juice (carbohydrates) and olive oil (fats) to balance the macronutrient profiles (amounts need is shown in Table 2). The macronutrient profile will be ~11% protein, ~65% carbohydrates, and ~24% fats, as recommended by the Institute of Medicine (Manore, 2005). All interventional meals will contain 6-13g of fiber which is within normal per-meal fiber range (Table 1).

CP1: Chickpeas, Quinoa, Quorn, and Bread (DIAAS 105)		
Baker's Mango and Passionfruit juice	245	ml
Olive oil	15	ml
CP2: Chickpeas, Quinoa, Tofu, and Bread		
Baker's Mango and Passionfruit juice	140	ml
Olive oil	13	ml
CP3: Chickpeas, Quinoa, and Bread		
Baker's Mango and Passionfruit juice	7	ml
Olive oil	12	ml

Table 2: An overview of the number of juice (carbohydrates) and olive oil (fats) to balance the macronutrient profiles for every experimental meal to reach ~810 kcal.

Form and dosage

The meals will be ingested orally on-site and calibrated to meet the per-meal protein requirement (0.27 g/kg) for light to moderate physically active individuals (FAO, 2001). As 80% of total energy is assumed to be derived from larger meals (snacks subtracted), the calculated per-meal protein requirement is: $1.0 \text{ g/kg/d} \times 0.80 \text{ (80\%)} = 0.80 \text{ g/kg/d}$. Assuming that three larger meals are consumed daily, 0.8 g/kg/d is divided by three = 0.27 g/kg/meal , resulting in 22g protein/meal for the average weight of the NZ population (80.5 kg) (MoH, 2017-2020: body size). The 1.0 g/kg/d to calculate the per-meal requirements was derived from reviewed literature for light to moderate physically active individuals (Park et al., 2021; Luiking et al., 2005; Tang et al., 2009; Volek et al., 2013; Pinckaers et al., 2022). The calculation of the per-meal IAA requirements was adjusted with a correction factor of 1.52 (1.0 g/kg/d divided by $0.66 \text{ g/kg/d} = 1.52$) (Table 3) as the FAO 2013 IAA requirements (mg/kg/d) is based on the 0.66 g/kg/d model, and a 1.0 g/kg/d model is used in this study.

IAAs	FAO (2013) IAA requirements, mg/kg/day	FAO (2013) IAA requirements, mg/day	FAO (2013) IAA requirements, mg/meal	IAA requirements (CF), mg/meal
Threonine	15	1208	322	488
Valine	26	2093	558	846
Isoleucine	20	1610	429	651
Leucine	39	3140	837	1268
Phenylalanine (AAA)	25	2013	537	813
Tyrosine (AAA)				
Histidine	10	805	215	325
Lysine	30	2415	644	976
Methionine (SAA)	15	1208	322	488
Cysteine (SAA)				
Tryptophan	4	322	86	130

Table 3: The numbers are based on an 80.5 kg individual. The corrected IAA requirements (mg/meal) are the FAO IAA requirements per meal multiplied by the correction factor (CF) 1.52. AAA: aromatic amino acids, SAA: sulfur amino acids, IAAs: indispensable amino acids.

13.1.2 Quality control

The investigators will perform quality control, ensuring that the food items are within the expiry dates and in good condition (no breaches). All foods will be commercially bought from the same brand and supplier throughout the study.

13.1.3 Packaging and labelling

The food items will be packed with the identity of treatment and frozen on-site or dry-stored depending on the food item need. Unique codes are placed on each food item according to the sequence code (13.1.5).

13.1.4 Randomization technique and coding

The participants and investigators will be aware of the treatment assignments. Three abbreviation codes will be applied. The codes will be (CP1) Quinoa, Quorn, chickpeas, and bread, (CP2) Chickpeas, quinoa, tofu, and bread, and (CP3) Chickpeas, quinoa, and bread. The abbreviations are CP1, CP2, and CP3. Participants will be allocated to sequences based on the Youden square design. The randomization list with participant number and the code sequence will be shared with the study investigators to select the abbreviation label for each participant on each intervention day.

13.2 Study product administration

13.2.1 Amount, composition, and preparation

As mentioned above, one of three meal conditions will be ingested once within 15 min, along with 300 ml of water, followed by blood sample collection. The investigators will prepare the meals on-site in a research kitchen under hygienic conditions. The amount of food being ingested will be 22g of protein, 132g of carbohydrates, and 22g of fats to meet the macronutrient composition stated in 13.1.1.

CP1, CP2, and CP3 contain chickpeas, tofu (only CP2), and Quorn (only CP1) will also be pan-fried. Quinoa will be simmered in water until cooked (approx. 10 min). All pan-fried foods will be seasoned with salt and paper in small quantities. The bread included in all interventional meals will be heated in an oven at 200°C for 5-10 minutes.

Other interventional foods that makeup the isocaloric cut-off of 810 kcal will be served cold and as fluid (uncooked).

The controlled pre-intervention evening diet, consisting of dinner (pre-packed), snack (muesli bar), and fluid (300 mL water) will be commercially bought from the same supplier throughout the study. The macronutrient composition will be 25g of protein, 70g of carbohydrates, and 30g of fats translating to 560 kcal. Participants are allowed 133 ml/hour if male, and 122 ml/hour if female during the 5.5-hour infusion period.

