16.3 Visit 1 (day 1)

It will comprise the completion of the first arm of the test protocol.

- Participants will report to the lab/clinic after an overnight fast between 7-9:00h.
 - The lab environment will be air-conditioned at 21-22°C.
 - Each participant will report at a consistent time across the study to account for circadian variability.
 - The stable isotope infusion protocol will last for 5.5 hours, during which participants will remain in a semi-supine or seated position. A calibrated syringe infusion pump will administer a primed-constant continuous infusion of stable isotopes via a catheter inserted into the antecubital vein in one arm and a second catheter will be inserted in a collateral dorsal hand vein to obtain arterialized-venous blood samples following the positioning of the hand in a customized heated-hand box (overview 16.5). The primary outcome measure for this study will be the determination of net whole-body protein balance, which will be assessed using the stable isotopes L-[Ring-²H₅]-Phenylalanine and L-[Ring-²H₂]-Tyrosine. Infusion rates for L-[Ring-²H₅]-Phenylalanine and L-[Ring-²H₂]-Tyrosine will be 270 μmol/h⁻¹ and 85.5 μmol/h⁻¹, respectively, with priming doses of 270 μmol and 85.5 μmol. To prime the phenylalanine-derived plasma tyrosine pool, a bolus dose of L-[Ring-²H₄]-tyrosine will be administered (prime = 23.25 μmol) (Jonker et al., 2014; Jonker et al., 2019). To measure splanchnic extraction, each meal will include oral ingestion of 84 mg of L-[¹⁵N]-Phenylalanine (half about halfway through meal and the rest at the end of the meal co-ingested with the juice). During the study at time point 0 minutes (preprandial), 30, 90, and 240 minutes (postprandial) the participants will be asked about sensory information in response to the meal on a 10 cm Likert scale. Participants are allowed 133 ml/hour if male, and 115 ml/hour if female during the 5.5-hour infusion period (Yamada et al., 2022).
-

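### Water is fixed at 300 ml while juice is 245, 140 and 7 ml, so drink volume at the meal (545, 440, 307 ml) is confounded with DIAAS in all three contrasts

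*Protocol*

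**What the plan says.** Section 13.2.1 sets the drink at the meal: "one of three meal conditions will be ingested once within 15 min, along with 300 ml of water, followed by blood sample collection". The 300 ml does not depend on the meal.

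Section 13.1.1 builds each meal to about 810 kcal "using juice (carbohydrates) and olive oil (fats) to balance the macronutrient profiles". Table 2 lists the juice:

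- CP1: "Baker's Mango and Passionfruit juice 245 ml"
- CP2: "Baker's Mango and Passionfruit juice 140 ml"
- CP3: "Baker's Mango and Passionfruit juice 7 ml"

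Table 1 gives the scores for CP1, CP2 and CP3 in that order: "DIAAS, % 105 75 50". Section 13.2.1 confirms that the items completing the 810 kcal are taken cold, as liquids.

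Drinking is also limited by the hour. Section 16.3 states: "Participants are allowed 133 ml/hour if male, and 115 ml/hour if female during the 5.5-hour infusion period". Section 13.2.1 gives the same allowance for men but 122 ml/hour for women. Neither section says whether the fluid taken with the meal counts toward it.

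**The concern.** The meals are matched on energy, protein, carbohydrate and fat so that protein quality is what varies, and the primary objective (section 10.1) attributes the response to stepwise increases in DIAAS. Drink volume is left unmatched, although water carries no energy or protein and could be varied without disturbing any matched quantity.

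The outcomes are read over a fixed 4-hour window after a meal eaten within 15 minutes. They include amino acid AUCs, glucose and insulin as well as PS, PB and NB. If the volume drunk affects how quickly a meal is delivered, part of a difference credited to DIAAS could come from the drink. Volume also rises with DIAAS, so an effect of volume could either add to the hypothesised gradient or mask it.

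**Working it through.** **Inputs.** Water: 300 ml for every meal (section 13.2.1). Juice: 245, 140 and 7 ml (Table 2). DIAAS: 105, 75 and 50% (Table 1). The protocol states no total fluid volume, so there is no planned figure to reproduce. As a check that Table 1 was read correctly, its energy rows add to the stated total: 88 + 524 + 198 = 810, 84 + 528 + 198 = 810, and 88 + 524 + 198 = 810 kcal.

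**Step 1: drink volume = water + juice.**

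| Meal | DIAAS, % | Water + juice, ml | Total, ml |
|---|---|---|---|
| CP1 | 105 | 300 + 245 | 545 |
| CP2 | 75 | 300 + 140 | 440 |
| CP3 | 50 | 300 + 7 | 307 |

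**Step 2: contrasts.**

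- CP1 − CP2: 545 − 440 = 105 ml
- CP2 − CP3: 440 − 307 = 133 ml
- CP1 − CP3: 545 − 307 = 238 ml

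Relative to CP3, CP1 is 545/307 − 1 = 78% higher and CP2 is 440/307 − 1 = 43% higher. The order is that of DIAAS. The correlation over the three meals is 0.99, but with three ordered points this adds little to the ordering.

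**Step 3: does water in the solid food reverse the order?** Moisture content is not given. The listed solids weigh 62 + 30 + 55 + 104 = 251 g (CP1), 147 + 44 + 22 + 26 = 239 g (CP2) and 230 + 54 + 23 = 307 g (CP3). Assume one common moisture share and count 1 g as 1 ml:

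| Assumed moisture | CP1 | CP2 | CP3 |
|---|---|---|---|
| 0% | 545 | 440 | 307 |
| 50% | 671 | 560 | 461 |
| 100% | 796 | 679 | 614 |

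The order holds throughout. The relative gap between CP1 and CP3 shrinks from 78% to 796/614 − 1 = 30%.

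**Step 4: can the design or model remove it?** Each meal brings its own volume in every sequence and every participant, so randomised order and within-subject comparison do not balance it. Section 18.6.1 has meal condition and time as fixed effects. A volume term would not help, because volume is fully determined by meal.

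**Step 5: does the hourly allowance close the gap?** Over 5.5 hours it permits up to 133 × 5.5 = 732 ml for men. For women it permits 122 × 5.5 = 671 ml or 115 × 5.5 = 633 ml, depending on the section. It is the same whichever meal is eaten, so it does not offset the difference at the meal unless meal fluid is counted against it, which is not stated.

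**Step 6: could the 300 ml include the juice?** Then water would be 300 − 245 = 55, 300 − 140 = 160 and 300 − 7 = 293 ml, and the volumes would be equal. The text does not say this. It specifies 300 ml of water alongside a meal of which juice is a component.

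**The case against.** The strongest reply is that no bias has been shown. Nothing in the protocol links drink volume to gastric emptying, amino acid appearance or net balance. That stands, and it limits the point to confounding.

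A reader might also set the 2.2 g smallest important change (section 18.2) against the 22 g of meal protein, get 2.2/22 = 10%, and infer that a shift of that share in protein handled within the window would produce a whole important difference. The documents do not support this. The 22 g is protein eaten and the 2.2 g is a change in net balance. Equating them assumes that every gram shifted becomes net balance, whereas the introduction (section 9) says amino acids in excess of the limiting one are oxidised. Nothing shows how much meal protein would still be undelivered at 240 minutes.

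Nor does volume track DIAAS exactly. The order is the same and the relation is close, but the inseparability comes from volume being fixed by meal, as is true of every meal component.

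Equal water with every whole-food meal is a defensible form of standardisation, and equal volumes would still leave the meals different. CP1 has 245 ml of juice and 62 g of bread against 7 ml and 230 g in CP3, fibre is 13, 7 and 9 g, and the oral phenylalanine tracer is co-ingested with very different amounts of juice. This is right, and the gain should not be oversold. It is not a reason to keep one further difference that can be removed.

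Finally, the hourly allowance covers the whole infusion, which starts 90 minutes before the meal (section 16.5). It is a ceiling, not a set intake. Over the 4 hours after the meal it permits men up to 133 × 4 = 532 ml, more than twice the 238 ml gap. Matching the meal drink alone therefore does not standardise all fluid, which is why the wording on the allowance also needs attention.

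**Conclusion.** The point holds as confounding. On the text as written, drink volume with the meal is 545, 440 and 307 ml for CP1, CP2 and CP3. It differs in all three contrasts, in the order of DIAAS, and the planned model cannot separate it from the meal effect. This rests on reading the 300 ml as water additional to the juice, which is what the wording says.

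It is a potential bias only. The size and direction of any effect on PS, PB, NB, amino acids, glucose or insulin cannot be derived from the protocol. The 78% excess of CP1 over CP3 refers to drinks alone. If the solids are counted in full it is 30%, with the order unchanged.

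The change is worth making because the alignment with treatment is certain and the remedy costs almost nothing. It would not by itself isolate protein quality.

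**What to change.** - In section 13.2.1, replace the fixed 300 ml with a water volume for each meal, so that juice plus water is one common total for CP1, CP2 and CP3. The sponsor chooses the total, which must be drinkable within the 15 minutes allowed.
- Add the three water volumes to Table 2. To illustrate the arithmetic only, a total of 545 ml would mean 300, 405 and 538 ml of water, and a total of 307 ml would mean 62, 167 and 300 ml. Either sets all three volume contrasts to zero. The two ends also show why drinkability needs checking: 538 ml of plain water would accompany the meal with the most bread.
- If the 300 ml was meant to include the juice, one clarifying sentence is enough.
- State whether meal fluid counts toward the hourly allowance, and reconcile the 122 ml/hour (section 13.2.1) and 115 ml/hour (section 16.3) figures for women.
- When interpreting the contrasts, acknowledge that juice versus bread and the juice volume carrying the oral tracer still differ between meals.

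The cost is a few sentences and one table row. The practical downside is that unequal amounts of plain water must be poured at each visit. No extra participants, samples or staff are needed.

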13.2.2 Familiarization trials

N/A.

13.2.3 Route of administration

Meals will be ingested orally on-site under investigator supervision within 15 minutes.

13.2.4 Subject compliance

Arrival on time or within reasonable limits. Ingesting meals within 15 min. Maintaining a normal diet and physical activity pattern within the intervention period with no strenuous or vigorous physical activity two days before interventions and comply with the controlled diet the day before intervention.

13.3 Study product handling

13.3.1 Storage and distribution

The interventional food items will be stored in a freezer and dry-stored on-site with limited access.

13.3.2 Study product accountability and reconciliation

The Investigator agrees not to supply the test food items to anyone except the subjects participating in this study.

14 ASSESSMENT OF EFFICACY

Efficacy will be assessed upon completion of the data collection and full statistical report and will be addressed according to the primary and secondary objectives listed above.

15 ASSESSMENT OF SAFETY

Safety will be continuously assessed based on the AE/SAE reporting and medical supervision ensured by the Principal Investigator or a designated person.

16 CONDUCT OF THE STUDY

16.1 Subject recruitment

A total of 8 men and women (67-77 years of age) will be required to complete the study, with contingency for another 2 if required due to dropout. The target is 4 in each gender, with contingency to complete 5 and 3 of either gender combination, depending on recruitment. Participants will be recruited from the local Auckland community via general advertisement at the University, University participant databases, social media, community notice boards, web pages, and word of mouth. Each participant will have the study outline and requirements explained in detail. At this point, they will be allowed to ask questions regarding the study and answer a health questionnaire. An inclusion checklist will be completed after the subject has agreed to participate by signing the consent. Subjects will be enrolled after fulfilling all inclusion criteria and presenting none of the exclusion criteria.

16.2 Visit 0 (day 0)

In-person screening will be conducted during the visit (V0), and consent will be obtained. Afterward, baseline parameters (personal data, history, anthropometric measures, and HbA1c) will be recorded with instructions.

HbA1c will be analysed via a Cobas B 101 system with finger prick blood collection. This process enables the measurement of HbA1c levels, ensuring they fall within the designated inclusion range. All evaluations will take place after the signing of informed consent. In addition, each participant will be required to answer three questionnaires to collect data on habitual protein intake, attitudes towards consumption of meat and meat alternatives, and sustainable diet patterns.

16.3 Visit 1 (day 1)

It will comprise the completion of the first arm of the test protocol.

- Participants will report to the lab/clinic after an overnight fast between 7-9:00h.
 - The lab environment will be air-conditioned at 21-22°C.
 - Each participant will report at a consistent time across the study to account for circadian variability.
 - The stable isotope infusion protocol will last for 5.5 hours, during which participants will remain in a semi-supine or seated position. A calibrated syringe infusion pump will administer a primed-constant continuous infusion of stable isotopes via a catheter inserted into the antecubital vein in one arm and a second catheter will be inserted in a collateral dorsal hand vein to obtain arterialized-venous blood samples following the positioning of the hand in a customized heated-hand box (overview 16.5). The primary outcome measure for this study will be the determination of net whole-body protein balance, which will be assessed using the stable isotopes L-[Ring-²H₅]-Phenylalanine and L-[Ring-²H₂]-Tyrosine. Infusion rates for L-[Ring-²H₅]-Phenylalanine and L-[Ring-²H₂]-Tyrosine will be 270 μmol/h⁻¹ and 85.5 μmol/h⁻¹, respectively, with priming doses of 270 μmol and 85.5 μmol. To prime the phenylalanine-derived plasma tyrosine pool, a bolus dose of L-[Ring-²H₄]-tyrosine will be administered (prime = 23.25 μmol) (Jonker et al., 2014; Jonker et al., 2019). To measure splanchnic extraction, each meal will include oral ingestion of 84 mg of L-[¹⁵N]-Phenylalanine (half about halfway through meal and the rest at the end of the meal co-ingested with the juice). During the study at time point 0 minutes (preprandial), 30, 90, and 240 minutes (postprandial) the participants will be asked about sensory information in response to the meal on a 10 cm Likert scale. Participants are allowed 133 ml/hour if male, and 115 ml/hour if female during the 5.5-hour infusion period (Yamada et al., 2022).
-

16.4 Visits 2-3 (days approx. 8 to 15)

- A repeat of Visit 1 but with another randomized order of treatment, allowing for a minimum period of 7 days of washout between visits to minimize any carry-over effects.

16.5 Biological samples

Arterialized venous blood will be collected from a dorsal hand vein heated hand method in a Perspex chamber (~55°C air temperature) (Gallen and Macdonald 1990). Blood samples will be collected from a superficial dorsal vein of the hand and placed in a thermostatically controlled box to mimic arterial samples (time points for blood sample collection can be viewed in Figure 1). Triplicate arterialized-venous blood samples will be collected at -20, -10 and 0 minutes after the infusion begins to measure pre-prandial enrichment of amino acids and glucose and insulin plasma concentrations. Post-prandial measurements will be collected between time 0-240 minutes. Each intervention will involve a protein meal given 90 minutes after the start of the infusion, and approximately 140 mL of blood will be collected per intervention. An overview of the infusion protocol is provided below (Figure 1).

[figure not shown]

Figure 1. Overview of the study protocol. In randomized order, participants receive one of the five meals at time=0 (x). A primed continuous infusion of Phe and Tyr stable isotopic tracers is used to calculate whole-body protein synthesis, breakdown, and net balance of the 4-h post-prandial period.

Blood samples will be collected and placed in heparinized tubes to prevent clotting. To minimize potential reactions, the samples will be immediately placed on ice, followed by deproteinization of the blood plasma with Trichloroacetic (TCA) (Appendix 2), the remaining untreated blood plasma will also be collected. The deproteinized and untreated plasma will be frozen and stored at -80°C until further analysis. To analyse the samples, we will use a liquid chromatography-electrospray ionization-tandem mass spectrometry quadrupole-time of flight (LC/MS-QTOF) system to determine isotope tracer enrichments, concentrations, and insulin. The amino acid enrichment will be expressed as a tracer:tracee ratio corrected for natural background abundance. An automatic analyser will determine plasma glucose concentrations. We analyse the samples in batches to minimize potential variability, and all procedures follow established protocols and guidelines. Quality control measures will be taken throughout the analysis to ensure the accuracy and precision of the results. Additionally, some blood samples might be analysed overseas.

